Participants will be randomised to either the control group (standard care) or the intervention group (standard care plus use of a StepIt pedal) for 12 weeks or until ulcer healing has taken place. Patients in both groups will be given the usual leg ulcer information leaflet, but those in the intervention group will be issued with a StepIt Pedal to use daily for foot and ankle exercises. These exercises consist of resisted plantar flexion while seated, performed 2 times daily in the pattern of: 1 minute exercise / 1 minute rest, 10 times (participants may alternate legs as an alternative to merely resting both legs for 1 minute). The participants will be asked to keep an exercise diary to record their activity. At their discharge visits participants are asked to provide their opinion on trial participation. All participants will have demographic data obtained and the following base line measures (table 2):

- VLU size measured with Convatec grid tool
- PUSH score (size and characteristics)
- Mobility score
- Ankle range of motion using a goniometer
- Visual analogue pain score
- Quality of life assessment using the Charing Cross Venous Ulcer Questionnaire

Table 3. Baseline measures

Weeks	0	2	4	6#	8	10	12#
Ulcer size and PUSH score	Х			Χ			Χ
Mobility score	Χ			Х			Χ
Ankle range of motion	Χ			Х			Χ
Visual analogue pain score	Χ			Χ			Χ
Charing Cross Venous Ulcer Questionnaire	Х			Х			Χ

Allowed to be up to 2 weeks early or late

The Pressure Ulcer Scale for Healing (PUSH) tool, see Appendix 1 is a standardised method of assessing and monitoring the severity and healing of both pressure ulcers and venous leg ulcers (Stotts et al, 2001; Ratliff & Rodeheaver 2005). Concerns have been raised regarding the criterion validity and intra-rater reliability of the tool (Pillen et al 2009) however in the absence of other valid tools it provides a comprehensive parallel assessment of the ulcer along with measuring size alone.

A mobility measure will be taken using a life space questionnaire, see Appendix 1 (Stalvey *et al* 1999). This is a tool that has demonstrated reliability and construct and criterion validity in establishing the spatial extent of an older person's mobility within their home setting. There are other versions (Peel *et al* 2005) that additionally measure the use of aids and equipment however this is not of particular interest within the study, hence the simpler version will be used.

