A recent review of specific health related quality of life instruments for venous leg ulcers favours the Charing Cross Venous Leg Ulcer Questionnaire (appendix 2) (Smith *et al* 2010) above others such as the Hyland for its disease specific psychometric characteristics (Gonzalez & Verdu 2011).

During the recruitment process the research team acts as a contact point and coordinator for patients requiring information and support. If concerns are raised on participants (mental) wellbeing based on the home visits or outcome of the assessments, referral of patients/families on to other professional agencies will be done as appropriate and according to the Trust guideline.

5.4 **Follow-up**

Patients are in the study until the VLU is healed or for the maximum period of 12 weeks. The patient will be followed up as they would in normal clinical practice. The community nurse will redress the VLU as per routine care, and will conduct the measurement of the VLU (grid measurement and PUSH score). The researcher will visit the patient at baseline, week 6 and week 12 of study participation to randomise the patient, hand out the StepIt pedal, measure ankle range of motion and conduct the questionnaires.

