5.5 Outcome measures

5.5.1 **Primary outcome measures**

To assess the feasibility of conducting a full CRT in the future, the primary outcome measures are mainly:

Trial-related outcome measures

- Participants' compliance to StepIt exercise regime
- Recruitment and attrition rates, willingness of patients to be randomised, response rates to questionnaires, and degrees of missing data
- Testing of eligibility criteria and ability/willingness of clinical staff to partake in recruitment of participants
- Ability of sites and clinicians to recruit and randomise patients, irrespective of care setting
- To assess any training requirements
- Adequacy of duration of follow-up (e.g. in relation to VLU healing)
- Fitness for purpose of data collection methods including across and between care settings
- Adverse events

5.5.2 **Secondary outcome measures**

The primary outcome for this pilot trial will be the feasibility of conducting a full CRT in the future. However, this study also aims to provide preliminary results regarding the acceptability and efficacy of a simple StepIt pedal as an adjuvant therapy for on VLU healing.

Clinical outcome measures

• VLU size, measured with Convatec grid tool (outcome measure used for calculating potential power of this present study)

Confidential – This document and the information contained herein may not be reproduced, used or disclosed without written permission from Cumbria Partnership NHS Foundation Trust Page | 11

- Size and characteristics of VLU, determined with PUSH score
- Mobility score
- Ankle range of motion
- Pain score
- Quality of life score, determined with Charing Cross Venous Ulcer Questionnaire
- Exercise diary
- Participant opinion on trial participation
- Patient withdrawal rates due to change in management (e.g. need for surgery)
- VLU infection rates

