7. SAFETY

7.1 Potential risks & benefits to study participants

There is no anticipated personal safety risk associated with taking part in this study. If the research team learns of important new information that might affect patient's desire to remain in the study, he or she will be told. Appropriate precautions are in place to ensure medical and personal information is kept safe through adhering to appropriate governance regulations. Participants in the StepIt intervention group will be asked to do the StepIt exercise; this will take more time and effort compared to standard management (treatment as usual). Any adverse events will be recorded, as outlined in sections below.

For the participants in the control group there is no direct benefit in taking part in this study. They will be cared for in exactly the same manner as they normally would. For participants in the Step It intervention group, there may be benefits in terms of improved VLU healing compared to normal standard care. However, this has not yet been proven and established, and this study is aimed to assess this. Participants cannot claim payments, reimbursement of expenses or any other benefits or incentives for taking part in this research.

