7.3 Procedures for recording adverse events

All SAEs need to be reported to the sponsor/host Trust R&D within one working day of the investigator team becoming aware of them.

The only device to be in contact with the patient is the sterile swab provided by the hospital and employed by hospital staff only.

The relationship of each adverse event to the trial must be determined by a medically qualified individual according to the following definitions:

- Related: The adverse event follows a reasonable temporal sequence from swabbing. It cannot reasonably be attributed to any other cause.
- **Not Related**: The adverse event is probably produced by the participant's clinical state or by other modes of therapy administered to the participant.

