APPENDIX 1. TOOLS AND ASSESSMENTS

This appendix contains:

- The PUSH tool that will be used to assess each leg ulcer at base line and 2 weekly thereafter. (from Stotts et al, 2001)
- The mobility life space questionnaire that will be completed for each participant to confirm limited mobility at base line and at 12 weeks (from Stalvey et al 1999)
- The Charing Cross Venous Ulcer Questionnaire used to score VLU-related quality of life for each participant at baseline and at 12 weeks (from Hareendran et al, 2005)
- Visual analogue pain scale

NATIONAL
PRESSURE
ULCER
ADVISORY
PANEL

Pressure Ulcer Scale for Healing (PUSH) PUSH Tool 3.0

Patient Name	Patient ID#	
Ulcer Location	Date	

Directions:

Observe and measure the pressure ulcer. Categorize the ulcer with respect to surface area, exudate, and type of wound tissue. Record a sub-score for each of these ulcer characteristics. Add the sub-scores to obtain the total score. A comparison of total scores measured over time provides an indication of the improvement or deterioration in pressure ulcer healing.

LENGTH	0	1	2	3	4	5	Sub-score
X	0	< 0.3	0.3 – 0.6	0.7 – 1.0	1.1 – 2.0	2.1 – 3.0	
WIDTH		6	7	8	9	10	
(in cm²)		3.1 – 4.0	4.1 – 8.0	8.1 – 12.0	12.1 - 24.0	> 24.0	
EXUDATE	0	1	2	3			Sub-score
AMOUNT	None	Light	Moderate	Heavy			
TISSUE	0	1	2	3	4		Sub-score
TYPE	Closed	Epithelial Tissue	Granulation Tissue	Slough	Necrotic Tissue		
							TOTAL SCORE

Life Space Questionnaire

Interviewer: "I am interested in all the places that you have been within the last 2 weeks" [It is acknowledged that original paper states 'within the last 3 days']

1.	During the past 2 week where you sleep?	s have you been to other rooms of your home besides the r	oom
	1 =Yes	2=No	
2.	During the past 2 week your porch, patio, garag	s have you been to an area immediately outside your home ge?	, such as
	1 =Yes	2=No	
3.	During the past 2 week courtyard, garden, driv	s have you been to an area outside your home such as a yar eway?	rd,
	1 =Yes	2=No	
4.	During the past 2 week beyond your own prop	s have you been to places in your immediate neighbourhoo erty?	d but
	1 =Yes	2=No	
5.	During the past 2 week but within your town o	s have you been to places outside your immediate neighbor community?	urhood
	1 =Yes	2=No	
6.	During the past 2 week community?	s have you been to places outside your immediate town or	
	1 =Yes	2=No	
7.	During the past 2 week	s have you been to places outside of Cumbria?	
	1 =Yes	2=No	

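### Adverse events and venous leg ulcer (VLU) infections are named outcomes, but the protocol gives non-serious events and infections no stated route into the trial record

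*Protocol*

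**What the plan says.** **Outcomes.** Section 5.5.1 lists "Adverse events" among the primary (feasibility) outcome measures. Section 5.5.2 lists "VLU infection rates" among the secondary clinical ones. Section 8.2 includes an absence or low number of adverse events among the signs that a larger trial is indicated.

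**Who does what.** Section 5.4: "The researcher will visit the patient at baseline, week 6 and week 12 of study participation". The tasks given for those visits are randomising, issuing the pedal, measuring ankle range and running the questionnaires. For the time between visits: "The community nurse will redress the VLU as per routine care, and will conduct the measurement of the VLU", by grid and PUSH score.

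**When.** Table 3 places its five rows at weeks 0, 6 and 12. A note on weeks 6 and 12 reads "Allowed to be up to 2 weeks early or late". Appendix 1 differs for the ulcer score: "The PUSH tool that will be used to assess each leg ulcer at base line and 2 weekly thereafter".

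**Safety recording.** Section 7.1: "Any adverse events will be recorded, as outlined in sections below". Section 7.3 then states "All SAEs need to be reported to the sponsor/host Trust R&D within one working day of the investigator team becoming aware of them". It adds that a medically qualified person judges relatedness, and defines a related event by its timing after swabbing.

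**The concern.** An outcome needs someone to look for it, a definition, and a way for the finding to reach the trial database. For serious adverse events the protocol has at least a reporting rule. For non-serious events and ulcer infections it names no observer, no occasion and no form, and it does not define infection. This is trial conduct, not analysis detail that a statistical analysis plan could supply later. Events not written down at the time cannot be fully recovered afterwards.

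The direction matters. Incomplete recording can only lower the count, and section 8.2 treats a low count as support for going on. The gap therefore leans towards a favourable reading of a device that section 2 says is being used in VLU patients for the first time. Section 9 adds that there will be no trial steering committee, so the in-house team would be relying on the same incomplete record.

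**Working it through.** The protocol states no figure for event capture, so there is none to reproduce. The check has three parts.

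**1. Following each outcome through the protocol**

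| Place | Non-serious adverse events | VLU infection |
|---|---|---|
| 5.5 Outcome measures | Primary | Secondary |
| Definition | General definition in 7.2 | None found |
| Table 3 | No row | No row |
| 5.4, researcher's tasks | Not listed | Not listed |
| 5.4, community nurse's tasks | Not listed | Not listed |
| Instruments in Appendix 1 | No item | No item |
| 7.1 | To be recorded, procedure said to follow | Only as an adverse event |
| 7.3 | Relatedness rule only, written for swabbing | Same |
| 8.2 | Low number supports a larger trial | Not named |

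On the instruments: PUSH scores area, exudate and tissue type. The Charing Cross questionnaire asks about pain, discharge and daily life. The life space questionnaire asks about places visited. The exercise diary in 5.3 records activity. None yields an infection or an event with an onset date.

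**2. Gaps between research visits**

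Inputs: visits at weeks 0, 6 and 12 (section 5.4), with 2 weeks either way on the last two (Table 3 note).

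- Planned gap: 6 − 0 = 6 weeks and 12 − 6 = 6 weeks.
- Longest gap after baseline: 6 + 2 = 8 weeks.
- Longest gap between visits: (12 + 2) − (6 − 2) = 14 − 4 = 10 weeks.
- Taking each visit as early, on time or late (nine combinations), the longest gap in a patient's schedule runs from 6 to 10 weeks.

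The 10-week case needs one visit at its earliest limit and the next at its latest. Week 14 is also beyond the 12-week maximum participation in section 5.4. With the last visit at week 12, the longest gap between visits is 12 − 4 = 8 weeks.

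**3. Direction of the error**

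If a share c of true events reaches the record, the expected recorded count is c × (true count), with c at most 1. Any c below 1 biases the count low. The protocol gives neither the frequency of nurse contact nor the duration of events, and it has no rule for forwarding them. So c cannot be derived.

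**The case against.** The strongest reply is that research visits are not the only contact. The community nurse handles the wound in routine care and already supplies trial data. Appendix 1 implies a 2-weekly ulcer assessment. Section 7.1 commits to recording any adverse event, and serious events are reported on awareness rather than by visit. Table 3 is titled as baseline measures and also omits the diary, participant opinion and withdrawals, so a missing row proves little by itself. The drawing in Appendix 2 is not visible in the text available and might assign this task.

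Much of this stands, and it rules out some stronger readings.

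- *Most short events would be missed.* A reader might infer this by supposing that status is seen only at weeks 6 and 12. For an event of D weeks the share present at a visit is then 2D/12: 17% for 1 week, 33% for 2, 50% for 3 and 67% for 4. The implied loss of 67% to 83% for events of 1 to 2 weeks needs that assumed duration, no recall, and no other source. With a contact every 2 weeks, the Appendix 1 interval, a 2-week event always coincides with a contact and a 1-week event does so half the time. The protocol supports none of these as an estimate.
- *Gaps of 8 to 10 weeks are the plan.* They are window extremes; the plan is 6 weeks.
- *The exercise diary makes StepIt patients report more events.* The diary is for activity, and nothing says it prompts event reporting. No difference between arms is shown.
- *The serious-event clock must move to the nurse.* The protocol does not show this to be necessary. Section 5.2 allows for nurses outside the research team, so such a change would carry delegation and training costs.

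The reply does not fill the central gap. Seeing a wound is not recording an event, and no section has the nurse note or forward one. The 2-weekly PUSH conflicts with Table 3, so it cannot be relied on, and PUSH would not register infection anyway. The general promise in 7.1 rests on a section that does not deliver it.

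**Conclusion.** The point holds in this form: adverse events and VLU infection rates are named outcomes, and followed as written the protocol tasks nobody with collecting infections or non-serious events. The recorded counts are likely to be incomplete and biased low, and the adverse event count feeds the decision in section 8.2. The size of the loss cannot be derived from the protocol. What can be stated is a planned 6-week interval between research visits, with window extremes of 8 weeks after baseline and 10 weeks between visits.

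Two textual faults belong with it. The relatedness rule in 7.3 is written around swabbing, so it cannot classify events from pedal exercise. The ulcer assessment schedule differs between Appendix 1 and Table 3, which leaves open whether any fixed wound contact exists between research visits.

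The conclusion assumes that the Appendix 2 flowchart does not itself assign event enquiry. It assumes nothing about how long infections last or how often nurses visit.

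**What to change.** 1. Add a row to Table 3 and a sentence to section 5.4. In both arms, and in whichever care setting dressings are done, the nurse records two yes/no items at each routine redressing, each with an onset date: VLU infection by a definition stated in the protocol, and any other adverse event. Any yes is forwarded promptly to the research team.
2. State that the infection rate and the adverse event count are calculated from these records.
3. Replace the swab wording in section 7.3 with wording for the pedal exercise.
4. Reconcile the 2-weekly PUSH assessment in Appendix 1 with weeks 0, 6 and 12 in Table 3.

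The reporting clock for serious events can stay as it is.

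Cost: two items on a contact that already takes place, a short briefing for the nurses in each setting, and some text edits. No extra visit is needed. More events will probably be recorded than under the present text, which is the purpose.

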5.5 Outcome measures

5.5.1 **Primary outcome measures**

To assess the feasibility of conducting a full CRT in the future, the primary outcome measures are mainly:

Trial-related outcome measures

- Participants' compliance to StepIt exercise regime
- Recruitment and attrition rates, willingness of patients to be randomised, response rates to questionnaires, and degrees of missing data
- Testing of eligibility criteria and ability/willingness of clinical staff to partake in recruitment of participants
- Ability of sites and clinicians to recruit and randomise patients, irrespective of care setting
- To assess any training requirements
- Adequacy of duration of follow-up (e.g. in relation to VLU healing)
- Fitness for purpose of data collection methods including across and between care settings
- Adverse events

5.5.2 **Secondary outcome measures**

The primary outcome for this pilot trial will be the feasibility of conducting a full CRT in the future. However, this study also aims to provide preliminary results regarding the acceptability and efficacy of a simple StepIt pedal as an adjuvant therapy for on VLU healing.

Clinical outcome measures

• VLU size, measured with Convatec grid tool (outcome measure used for calculating potential power of this present study)

Confidential – This document and the information contained herein may not be reproduced, used or disclosed without written permission from Cumbria Partnership NHS Foundation Trust Page | 11

- Size and characteristics of VLU, determined with PUSH score
- Mobility score
- Ankle range of motion
- Pain score
- Quality of life score, determined with Charing Cross Venous Ulcer Questionnaire
- Exercise diary
- Participant opinion on trial participation
- Patient withdrawal rates due to change in management (e.g. need for surgery)
- VLU infection rates

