6. SUBJECTS

6.1 Anticipated number of research subjects

Since there is no pilot data to base an *a priori* sample size calculation on, it is difficult to make a calculated prediction on the exact number of patients required for a sufficiently powered trial. The outcome of this present study will inform the power calculation for a larger definitive interventional trial. However, below a summary is given for the power potentially achievable for our suggested feasibility sample size. Since some patients may require surgical intervention or may withdraw, a hypothetical 30% dropout rate is calculated into the sample size (actual attrition rate is a study objective). A 1:1 allocation to the control and intervention group respectively will be applied.

The primary outcome, average percentage decrease in ulcer size is used for sample size calculation. Power calculations for sample size, 80% power and 5% significance, based on a Chi-squared test. A priori power calculations using GPower 3.1 software, result in the following sample size summarized in Table 4.

It must be stressed that this current PREVUE study will first and foremost establish if StepIt exercise is acceptable to staff and patients alike, and therefore it is not certain at this stage whether sufficient participants will be enrolled, if participants will be compliant and if they will be compliant for the 12 weeks treatment period.

Table 4, Sample size calculation

	Percentage patients achieving at least 50% reduction in ulcer size	Percentage patients not achieving 50% reduction in ulcer size		
Arm A (hypothetical)	60%	40%		
Arm B (hypothetical)	30%	70%		
	Power beta of 80%, Alpha p-value of 0.05, Effect size 0.6 Sample size required without any drop-out: 22 samples. Sample size with 30% attrition rate included: 28			
	Total of 28 patients: - 12 Patients to receive treatm - 12 Patient to receive treatment	nent as usual ent as usual plus Steplt exercise		

The CONSORT guidelines require a statement on the number of patients assessed for eligibility (Schulz, Altman & Moher 2010). The number of patients screened but who did not meet the inclusion criteria or who declined to participate will be recorded, as will any patients who are lot to follow-up (Appendix 3).

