The calculation does take into account a 30% patient attrition rate (withdrawal and loss to follow-up), since this involves a study with at least two visits. Patients will be recruited from the adult (age 18+) population routinely seen by the evaluating clinical staff members.

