6.1.1 Randomisation

Following written consent patients will be allocated at random to the control or intervention group, using a non-restricted randomised sequence generated for the whole sample using a free ware randomisation programme, see https://www.randomizer.org/. The randomisation will be stratified for VLU size, with one group being those with a PUSH score of 8 or lower and the other with a PUSH score of 9 or higher. Sequential envelopes with each next randomisation allocation will be used to achieve concealment. It is recognised that random selection does not guarantee representativeness but variables which may affect the outcome variable are more likely to be balanced out and reliability enhanced (Thomas 1990).

As the study involves a self-administered intervention of necessity it is not possible to achieve blinding for the participants. Due to the pilot nature of this study, the researcher will not be blinded either to the subjects intervention, although this can be considered as part of a larger trial since it would further reduce any risk of bias. However, the primary outcome measure, size of the VLU is a quantitative outcome measure which is less prone to bias than for example a patient reported outcome measure or a clinician reported outcome measure.

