6.3 Early withdrawal of subjects

Patients have the right to withdraw from the trial at any time and without giving any reason. If a patient withdraws from the trial, any and all information gathered prior to the withdrawal will be excluded in the analysis, no further data collection will occur. If a patient does not attend a planned follow-up appointment then two more attempts will be made to contact the patient regarding the study. If still no contact can be made then the patient is deemed lost to follow-up and any collected study data will be retained.

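### Surgery is treated as withdrawal and as dropout, in conflict with follow-up to healing or week 12; the protocol should say that measurement continues after it

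*Protocol*

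**What the plan says.** Four parts of the protocol bear on a patient who needs surgery during the study.

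- **Section 5.5.2** lists among the secondary outcomes "Patient withdrawal rates due to change in management (e.g. need for surgery"). A change in management is thus named as a cause of withdrawal.
- **Section 6.1** explains the sample size allowance: "Since some patients may require surgical intervention or may withdraw, a hypothetical 30% dropout rate is calculated into the sample size". It later describes the same allowance this way: "The calculation does take into account a 30% patient attrition rate (withdrawal and loss to follow-up").
- **Section 5.4** gives the general duration rule: "Patients are in the study until the VLU is healed or for the maximum period of 12 weeks". Surgery is not mentioned as an exception.
- **Section 6.3** sets two data rules. For a patient who withdraws, "any and all information gathered prior to the withdrawal will be excluded in the analysis, no further data collection will occur". A patient who cannot be contacted is "deemed lost to follow-up and any collected study data will be retained".

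On assessment, Section 6.1.1 says that participants cannot be blinded and that "the researcher will not be blinded either to the subjects intervention". Section 8.3 compares changes in ulcer size and PUSH score between arms with a Mann-Whitney test. Section 8.2 rests the decision on a larger trial on several signals, including clinical effectiveness and low attrition.

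**The concern.** Sections 5.5.2 and 6.1 treat surgery as a way out of the study, while Section 5.4 keeps the patient in. A dropout allowance for surgery makes sense only if these patients are expected to give no outcome data. Site staff reading the protocol cannot tell whether to make the week 6 and week 12 visits for a patient who has had surgery and still consents.

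The choice matters because of Section 6.3. A patient handled as withdrawn loses both the later measures and those already taken. A patient handled as lost to follow-up keeps the earlier data. Section 6.1 describes the 30% as made up of just these two groups, and the text does not say which one a consenting surgery patient joins.

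If surgery tends to follow poor healing, and happens more often in one arm, removing these patients makes that arm look better. Knowledge of the allocation makes unequal exits possible. Measurements that were never taken cannot be recovered by a later analysis plan.

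**Working it through.** **The plan's own figure.** Section 6.1 gives 22 patients without dropout and 28 with 30% attrition. A chi-squared power calculation with 1 degree of freedom, effect size 0.6 and 5% significance gives 22 (power 80.4%). The 28 is close to 22 × 1.3 = 28.6. The protocol does not say how much of the 30% is surgery, so these figures cannot size the problem, and what follows is an illustration.

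**Set-up (assumptions).** There is no true effect, so both arms share one continuous distribution of healing. The 28 patients split 1:1 give n = 14 per arm. In one arm only, k patients leave through surgery and all their data are lost. The measure is the probability that a kept patient in that arm shows a better change than a patient in the other arm, where 0.50 means no difference. This is what the Mann-Whitney test assesses.

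**Case A: the k worst healers leave.** P = (n + k + 1) / (2(n + 1)).

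| k | n = 14 | n = 12 |
|---|---|---|
| 1 | 16/30 = 0.533 | 14/26 = 0.538 |
| 2 | 17/30 = 0.567 | 15/26 = 0.577 |
| 3 | 18/30 = 0.600 | 16/26 = 0.615 |

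The n = 12 column uses the per-arm number printed beside the total of 28. The Lay Summary gives 24 per arm, for which the formula yields 26/50 = 0.52, 27/50 = 0.54 and 28/50 = 0.56.

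**Case B: k patients leave at random from the worse-healing half (n = 14).** The expected rank values are i/15 and sum to 7 over the arm. The seven worst average 4/15 = 0.267. So P = (7 − 0.267k) / (14 − k).

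- k = 1: 6.733/13 = 0.518
- k = 2: 6.467/12 = 0.539
- k = 3: 6.200/11 = 0.564

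**Case C: leaving is unrelated to healing.** P = 0.50 for any k.

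**False-positive rate.** Exact two-sided 5% Mann-Whitney test, n = 14, 20,000 simulated trials per case, exits in one arm only:

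| k | Case A | Case B | Case C |
|---|---|---|---|
| 1 | 6.5% | 5.1% | 5.0% |
| 2 | 9.8% | 5.2% | 4.5% |
| 3 | 14.0% | 6.5% | 4.3% |

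**Exits in both arms (n = 14, simulated).** Equal exits (1 v 1 or 2 v 2) leave P at 0.50 under either selection model. Exits of 2 v 1 give about 0.54 with about 8% false positives for worst healers, and about 0.52 with about 4% for the worse half. Exits of 3 v 1 worst healers give about 0.57 and 12%.

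**The case against.** The strongest reply is that nothing tells staff to stop following a surgery patient. Section 5.4 states the only end-of-study rule, and surgery is not in it. Section 6.3 is worded for a patient who uses the right to withdraw. The Section 6.1 sentence is a planning remark that lists surgery beside withdrawal. A reader might infer that the protocol orders a surgery patient's data to be deleted. The documents do not support that: applying Section 6.3 to surgery is an inference, and the exclusion of earlier data applies to every withdrawing patient, whatever the reason. This part of the reply stands. What it leaves is the conflict itself, because Sections 5.5.2 and 6.1 suggest that these patients were expected to leave and no sentence says that their measures go on.

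A reader might also infer that the attrition estimate is spoiled. That is largely answered. Section 5.5.2 reports withdrawal for a change in management as its own outcome, and Section 8.2 reports reasons for discontinuation, so attrition can be computed with or without these patients. Each one stopped who would have stayed costs 1/28 = 3.6 points of week 12 retention, and the pilot would not show whether such patients can be kept. That is a minor point.

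A third reply is that this is a small feasibility study with ulcer healing as a secondary outcome and no numerical threshold for going on. That lowers the stakes but does not remove them. Section 8.2 uses signs of effectiveness in the decision and allows that a large effect might settle the question in this trial.

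Finally, which values enter the comparison after surgery can be left to an analysis plan. Whether the visits take place cannot.

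**Conclusion.** The concern holds as a conflict between sections with an avoidable risk of losing data. Sections 5.5.2 and 6.1 treat surgery as an exit, Section 5.4 does not, and handling it as withdrawal would remove the patient from the ulcer size and PUSH comparison altogether.

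Bias needs three things together: staff treat surgery as withdrawal, surgery is related to poor healing, and its frequency differs by arm. The documents establish none of these. Lack of blinding makes unequal exits possible but is not evidence of them. The 14% false-positive rate should not be read as an expected value, since it needs 3 of 14 patients (21%) to have surgery in one arm, none in the other, and those three to be the worst healers. In the milder case the error rate stays close to 5%, though the probability still shifts by 0.018 to 0.064.

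Severity is low to moderate. The change is worth making because it decides which data exist.

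**What to change.** In Sections 5.5.2 and 6.3, state that:

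- a change in management such as surgery is not in itself withdrawal from the study;
- the planned week 6 and week 12 measures continue unless the patient withdraws consent;
- data already collected on such a patient are kept;
- the change in management and its date are recorded, by arm.

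Reword the Section 5.5.2 outcome as the rate of change in management, so that it no longer implies an exit.

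The cost is a wording amendment. The visits are already scheduled, and Table 3 in Section 5.3 gives room around each follow-up visit: "Allowed to be up to 2 weeks early or late". The downside is that ulcer measurements after surgery also reflect the surgery, so add a sensitivity display of the ulcer results without those values.
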